The overarching aims of the proposed trial are to determine the safety and immunogenicity of CH505 EnvSeq-1 vaccine administered in combination with the GLA-SE adjuvant. The specific aim of Part A of the study is to make a rational choice for the optimal dose of gp120 Env protein that will be used in the other groups. The dose-ranging study of this vaccine product with GLA-SE in NHP (NHP 106; see Section 4.8.1 on Preclinical immunogenicity studies) demonstrated that after the second injection there was clearly a hierarchy of doses with respect to inducing Env binding as well as neutralizing antibodies and thus, the first part of this study will be a critical first step leading to the selection of a protein dose in humans and to Part B of the trial. The other important aspect of Part A is to evaluate the immunogenicity of CH505TF gp120 and compare to responses induced with the different combinations of the 4 Env mutant proteins in order to assess whether Env mutants, and not just CH505TF gp120 alone, are

needed to induce the desired lineage. The second part of the study will allow us to focus in on the essence of the concept of how to induce the desired bnAb pathways. And thus, the aims of the second part of the strategy (Part B) will be to assess the ability of the CH505 gp120 EnvSeq-1 mutant variants to induce CD4-binding site bnAb lineages. The EnvSeq-1 proteins will be administered either by combining the proteins with an additive approach with overlapping exposure to antigens (mimicking the coexistence of antigens in the environment in which they evolved naturally) and in a sequential immunization approach with each of the proteins administered separately in the order in which they evolved. An important secondary objective will be to explore the repertoire of B cell responses and isolate clones of the desired bnAb lineage.

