chosen for the dose in the arms of Part B will be determined by analysis of antibody binding data from a validated assay and will additionally be informed by the assay of memory B-cell receptor binding to CH505TF gp120 and differential binding to the CH505 I $\Delta$ 371 gp120 Env. Preliminary data from the NHP 106 study included both plasma antibody and flow cytometric quantification of memory B cells that displayed differential binding; analysis of both measures indicated that 300 mcg/dose was optimal in NHP. For that reason, we expect that the validated assay primary outcome data and the secondary outcome data from flow cytometry will give a concordant answer.

**Figure 4-12. Inhibition of CH106 CD4 bs binding to B.63521 gp120 Env by NHP 106 plasma from immunization with 5 different doses of CH505TF gp120.**

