To address antibody endpoints in Part A, the analysis will descriptively summarize binding response positivity call rates, and test superiority of the frequency of differential memory B cell binding (to wild type vs mutant  $\text{I}\Delta 371$  CH505) and of the magnitude and breadth of the IgG binding Ab response to a panel of gp120 proteins for each of 2 comparisons (Group 1 vs 2, and Group 2 vs 3), using a two- sided Wilcoxon rank sum test with 5%/2 type-I error rate per comparison. The sample size of 12 vaccinees per group will give 80% power to detect a true difference of 1.81 standard deviations (SDs) between the mean responses and 90% power to detect a true difference of 2.04 SDs. Using the mean and SD values from the HVTN 088 trial, the difference of 1.81 SDs translates to a difference of 0.708 units of  $\log_{10}$  binding magnitude; if 1 of the comparison groups has the same mean as was seen among non-negative values among vaccine recipients in the HVTN 088 trial (4.06 units), then after incorporating the expected 6% zero-valued (negative responder) measures, this corresponds to observing an increase or decrease in the overall mean from 3.691 in group 1 to 4.336 in group 2. These calculations assume a 10% loss-to-follow-up rate and the (94%) response rate observed in the HVTN 088 vaccine recipients. The same approach will be used to test superiority of the magnitude of the IgG binding Ab response to each individual gp120 antigen in the panel.

To address antibody endpoints in Part B, the analysis will descriptively summarize binding and neutralization response positivity call rates and test superiority of the frequency of differential memory B cell binding and of magnitude and breadth of the IgG

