To test for differences among the vaccine arms in Part A and separately in Part B, first a Kruskal-Wallis rank test or an F-test (depending on the normality assumption) will be used to test for overall differences. Secondly, if the overall test is significant at the 2-sided 0.05 level, then individual tests comparing the 2 adjacent pairs of vaccine arms (Part A) and all 6 pairs of 4 vaccine arms (Part B) will be done unless pre-specified. If rank-based tests are used then the tests will be inverted to construct Hodges-Lehmann point estimates and 2-sided  $(1-0.05/k) \times 100\%$  CIs about the differences in location centers of the  $k = 2$  (Part A) or  $k = 6$  (Part B) pair-wise comparisons of vaccine arms. If actual-value tests are used then the Dunnett's procedure will be used to construct simultaneous confidence intervals about the pairs of mean differences for the many-to-one comparisons [62] when multiple vaccine arms are each compared with 1 common control arm. When all pair-wise comparisons between the multiple vaccine arms are of interest, the Tukey procedure [63] will be used. If only specific comparisons between pairs of the multiple vaccine arms are of interest, the Holm-Bonferroni procedure will be used. An appropriate data transformation (eg,  $\log_{10}$  transformation) may be applied to better satisfy assumptions of symmetry and homoscedasticity (constant variance). Significance of the differences between pairs will be evaluated using 2 procedures, first based on whether the simultaneous 95% CIs exclude zero and secondly based on whether the nominal (unadjusted) 95% CIs exclude zero.

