### 6.4.4.5 Analysis of multiplexed immunoassay data

When a small panel of analytes (eg,  $\leq 5$ ) is being assessed in a multiplexed immunoassay, the analysis of response rates and response magnitudes will be evaluated and compared as described under the general approach. Details for calculating a positive response and response magnitude will be provided in the SAP. When a larger panel is being assessed, 2 approaches may be considered to evaluate the magnitude and breadth of these responses. First, Magnitude–Breadth (M-B) curves maybe employed to display individual- and group-level response breadth as a function of magnitude. Response breadth of neutralizing antibodies is defined as the average of the  $\log_{10}$  NAb titer over the panel of isolates, where titers that are below the limit-of-detection are set to half of that limit. Response breadth of binding antibodies is similarly defined as the average of the response over the panel of antigens. Two choices are to compare the M-B curves among vaccine arms, as follows: a non-parametric Wilcoxon rank sum test on the subject-specific area-under-the M-B curve (AUC M-B) or a Kolmogorov-Smirnov type test on the 2 group-average M-B curves. Simulations can be used to obtain 2-sided p-values for the latter test. Second, a weighted-average score-like variable may be constructed to account for the correlations between analytes as an integrate magnitude of responses to multiple analytes. Similar group comparison methods described in the first approach may be adopted. Details of either approach will be described in the SAP.

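### Part A's rank-based plan compares only adjacent doses at 2.5% each, gives no 20 vs 400 mcg estimate or trend test, and does not say which confidence interval decides

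*Combined protocol and SAP*

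**What the plan says.** - **Purpose.** Section 4.1.2: "The specific aim of Part A of the study is to make a rational choice for the optimal dose of gp120 Env protein". Section 4.8.1 says that the dose "chosen for the dose in the arms of Part B will be determined by analysis of antibody binding data from a validated assay", informed also by memory B-cell binding. Section 4.5 adds safety data.
- **Comparisons and level.** Section 6.1.2 tests superiority of IgG binding magnitude-breadth "for each of 2 comparisons (Group 1 vs 2, and Group 2 vs 3"), by two-sided Wilcoxon test at 5%/2 per comparison. It states 80% power at 1.81 SD and 90% at 2.04 SD, and expresses the former as a shift in the "overall mean from 3.691 in group 1 to 4.336 in group 2". No overall test is mentioned there.
- **Overall test, then pairs.** Section 6.4.4.1 begins with a Kruskal-Wallis or F-test. If that is significant at 0.05, the next step is "individual tests comparing the 2 adjacent pairs of vaccine arms (Part A) and all 6 pairs of 4 vaccine arms (Part B"). The sentence closes with a qualifier that is not explained: these tests "will be done unless pre-specified". For rank-based tests it gives Hodges-Lehmann estimates and intervals with k = 2 in Part A.
- **Deciding interval.** Significance of a pair is judged first by simultaneous intervals and "secondly based on whether the nominal (unadjusted) 95% CIs exclude zero". Neither is named as decisive.
- **Other routes.** Tukey all-pairs intervals appear in Section 6.4.4.1 only for actual-value tests. Section 6.4.4.5 adds, for larger panels, "Two choices are to compare the M-B curves among vaccine arms, as follows" (a Wilcoxon test or a Kolmogorov-Smirnov type test), with details left to the SAP.

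**The concern.** There are three doses, so there are three pairs, and the plan leaves out the widest one. If binding rises gradually with dose, each adjacent step is only part of the whole effect. The overall test can then show that dose matters while neither planned pair reaches 2.5%, and the plan provides no estimate or interval for 20 against 400 mcg.

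Two rules are also open. The phrase about pre-specification leaves it unclear whether the overall test gates the pairs that Section 6.1.2 names. And where the simultaneous and nominal intervals disagree, the conclusion depends on a choice that is not written down. These data are the main immunogenicity input to the Part B dose, so the formal reading should be fixed in advance.

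**Working it through.** **Inputs (Section 6.1.2).** 12 per group; 10% missing; 94% non-zero responses; non-zero mean 4.06 and SD 0.391 on the log10 scale; two-sided Wilcoxon at 0.025.

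**Reproducing the plan's figures.**
- Evaluable per group: 12 × 0.9 = 10.8, taken as 11.
- Shift: 1.81 × 0.391 = 0.708, as stated.
- Overall means: 4.06 × 10/11 = 3.691, and (4.06 + 0.708) × 10/11 = 4.335 against 4.336 stated. The plan's means therefore correspond to one zero among 11 (9.1%). Zeros at 6% would give 4.06 × 0.94 = 3.816 and 4.768 × 0.94 = 4.482.
- Simulated power for one pair with exactly one zero per arm: 79% at 1.81 SD and 90% at 2.04 SD. With random 6% zeros: 80% and 87%. The stated 80% and 90% stand.

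**Set-up for the gap.** Three arms of 11; Kruskal-Wallis at 5% with tie correction; pairwise Wilcoxon by normal approximation without continuity correction; 60,000 trials per scenario. The assumed shape is linear in log dose, so the 100 mcg arm has ln(5)/ln(20) = 0.537 of the total 20-to-400 mcg effect. This shape and the effect sizes are assumptions.

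Percentage of trials, random 6% zeros / exactly one zero per arm:

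| Total effect | Overall test significant | Overall significant, no adjacent pair at 2.5% | Overall significant, no adjacent pair by nominal 95% CI |
|---|---|---|---|
| 1.0 SD | 37 / 25 | 19 / 17 | 12 / 10 |
| 1.5 SD | 68 / 62 | 32 / 40 | 19 / 22 |
| 1.81 SD | 83 / 81 | 32 / 47 | 17 / 23 |
| 2.5 SD | 97 / 99 | 17 / 30 | 7 / 10 |
| 1.81 SD per step | 99 / 100 | 2 / 2 | under 1 / under 1 |

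**What the third pair adds (1.81 SD total).** Probability of at least one significant pair after a significant overall test:
- adjacent pairs at 2.5%: 51% / 34%
- adjacent pairs at 5%: 66% / 58%
- all three pairs at 5%: 83% / 81%

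With random zeros, 66 − 51 = 15 points come from dropping the 5%/2 split and 83 − 66 = 17 points from Group 1 vs 3 alone. With one zero per arm, the corresponding gains are about 24 and 23 points. At this effect the two interval readings, taken after the overall test, disagree on whether any adjacent pair is significant in 15% / 24% of trials.

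**Other shapes, 1.81 SD total.** Adjacent pairs at 2.5% against three pairs at 5%, both gated: a single step from 20 to 100 mcg, about 80% against 92–93%; 80% of the effect reached by 100 mcg, 57–65% against 86–88%.

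**Error control.** With three arms, equality in any two pairs implies equality of all three. The overall null is therefore the only intersection hypothesis, and an overall 5% test followed by each pair at 5% is a closed procedure. Simulated family-wise error for the gated three pairs: 4.8% / 1.5% under the global null, and 4.7–4.9% / 2.2–2.4% with one true null pair. For the adjacent pairs at nominal 5% without a gate, under the global null: 8.7% / 4.4%. With a gate: 3.9% / 1.3%. The argument does not carry to Part B's four arms, where two disjoint pairs can be equal without all four being equal.

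**The case against.** The adjacent pairs match the decisions to be made (20 or 100, 100 or 400 mcg). A significant 20 vs 400 mcg result alone does not separate neighbouring doses, and naming two contrasts at 12 per arm is a defensible design. This stands, and it limits what the third pair can deliver.

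The level of 5%/2 in Section 6.1.2 points to the k = 2 simultaneous interval as the deciding one. That is a fair reading, but Section 6.4.4.1 also evaluates significance by nominal intervals and does not call them supportive. The ambiguity over the gate itself matters little: applying it costs the 2.5% rule at most about 1 point of power.

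The size depends on the assumed dose-response. In macaques, Section 4.8.1 reports similar binding at all doses after three immunizations, which is the Part A timing, yet also calls 300 mcg optimal. That evidence is mixed and fixes no human effect size.

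The plan also has other tools: box plots and reverse cumulative curves for all arms, a possible two-part test, Tukey intervals on the parametric route, and details deferred to the SAP. These could show or test 20 against 400 mcg, but Section 6.1.2 names the Wilcoxon test on adjacent pairs for this endpoint.

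A reader might infer that nearly half of trials would end with an unattributed dose effect. The 47% figure lies near the peak over effect sizes and uses 9.1% zeros in place of the planned 6%. A reader might also infer that the plan inflates family-wise error. That holds only for the nominal reading without the gate, and only when zeros vary at random.

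**Conclusion.** The point holds in a limited form. On the rank-based route Part A has no planned estimate, interval or test for 20 vs 400 mcg and no trend test, and the ranking of the two interval readings is not stated. For a graded effect of 1.0 to 1.81 SD in total, about 19% to 32% of trials would show an overall dose effect with no adjacent pair significant at 2.5% (12% to 19% by nominal intervals). With exactly one zero per arm the 2.5% range is 17% to 47%. The problem nearly vanishes at 1.81 SD per step. If the overall test is binding, the 5%/2 split is not needed to control error among three arms.

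The documents do not support the stronger inferences that the power statements are wrong or that the dose choice is blocked. The powers reproduce, no p-value rule for the dose is stated, and the choice also draws on memory B-cell and safety data. This is a cheap improvement of modest severity.

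**What to change.** In Sections 6.1.2 and 6.4.4.1, for Part A only, state the following:

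- The overall test at two-sided 0.05 gates the pairwise tests, including the two named in Section 6.1.2.
- If it is significant, Groups 1 vs 2, 2 vs 3 and 1 vs 3 are each tested at two-sided 0.05 (closed procedure for three arms). This alone determines significance.
- Hodges-Lehmann estimates with nominal 95% intervals are reported for all three pairs. Any simultaneous intervals use k = 3.
- A significant Group 1 vs 3 result on its own shows a dose effect across the range and does not separate adjacent doses.

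A rank-based trend test may be added as supportive.

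The cost is wording in the protocol and SAP, with no new participants, samples or assays. Simultaneous intervals with k = 3 are about 7% wider than with k = 2 (normal multipliers 2.394 / 2.241 = 1.07). For the adjacent pairs, the gated 5% rule is never less powerful than the gated 2.5% rule, and the gate costs at most about 1 point against an ungated 2.5% rule. The change does not set a dose rule.

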### 6.1.2 Sample size calculations for immunogenicity

To address the humoral immunogenicity endpoints, the analysis will compare the area under the magnitude-breadth curve of the IgG Env binding Ab response, and will compare the frequency of memory B cells that bound to gp120CH505 TF but not to gp120CH505 TF  $\Delta$ 371, 2 weeks after the third (Part A) or fourth and sixth (Part B) vaccinations with CH505TF gp120. To estimate power, binding magnitude-breadth data were simulated assuming that the proportion of non-zero responses was 0.94 in both comparison groups. This is based on pilot data for the IgG binding Ab response in HVTN 088. For these calculations, non-zero responses, modeled on the  $\log_{10}$  scale, were drawn from a normal distribution. The mean non-zero response in group 1 was set to 4.06. This was the mean non-zero response in the HVTN 088 vaccine arm T2 (the treatment arm for vaccine naïve participants). The standard deviation (SD) of the non-zero response was set to 0.391 for both groups; this was the SD of the non-zero response in the HVTN 088 vaccine arm.

The differential binding rate is the fraction of class memory B cells that have the property of binding the two protein hooks in a differential manner (defined by flow gating). In the assay, two measurements are made simultaneously: binding to the transmitted founder CH505 virus, and binding to the  $\text{I}\Delta 371$  variant. Each of these yields a measurement of the proportion of memory B cells that bind to a target virus. While the primary interest is in the differential binding to these two viruses, which is the difference of these proportions, we will also evaluate each measure separately to further describe and explore the relationship between these measures under the scenarios represented by the arms of this trial.

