Power for this is high if we can pool the cells across participants, which would be possible under an assumption of a homogeneous rate of differential binders across participants within a treatment group. Our prior expectation is that this is at least approximately correct, though we will evaluate the homogeneity and if we find evidence for different rates across participants, we will revert to the more conservative approach of treating participant rates of differential binders as varying across participants around a common group mean. In case pooling is not justified, power is the same (on the per-SD scale) to that calculated for binding Abs, since preliminary data indicate that the log-transformed rates of differential binding are consistent with the normal distribution.

However, interpretation of these SDs differs between the differential binding rate power calculations and the power calculations for the primary antibody endpoints. In the case of binding Abs, the SDs are on the scale of log-transformed binding Ab response values (which are areas under the magnitude-breadth curve), so it is reasonable to describe these in terms of "fold changes". However for differential binding Abs, the values and SDs are fractions. So for instance, if the SD is .001 (equivalently, 0.1%) that means that there is 90% power to detect a 0.2% difference between the differential binding rates in the two arms. In the text below we provide example interpretations of the SDs for the context of the primary Ab binding endpoints only.

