binding Ab response to a panel of gp120 proteins and of the neutralization of tier 1 and tier 2 panels of HIV-1 viruses. Each analysis will be conducted separately for each of 2 pooled comparisons (additive vs sequential, pooling over groups with and without mosaic DNA: Groups 5 and 6 combined vs Groups 7 and 8 combined; effect of mosaic DNA, pooling over groups receiving additive and sequential proteins: Groups 5 and 7 combined vs Groups 6 and 8 combined), and for each of 6 pairwise comparisons among these groups using a two- sided Wilcoxon rank sum test with 5% type-I error rate per pooled comparison and a 5%/6 type-I error rate per pairwise comparison. The sample size of 20 vaccinees per group will give 80% power to detect a true difference of 1.63 standard deviations (SDs) between the mean non-zero responses and 90% power to detect a true difference of 1.81 SDs for the pairwise comparisons. Using the mean and SD values from the HVTN 088 trial, the difference of 1.63 SDs translates to a difference of 0.637 units of  $\log_{10}$  binding magnitude; if 1 of the comparison groups has the same mean as was seen among non-negative values among vaccine recipients in the HVTN 088 trial (4.06 units), then after incorporating the expected 6% zero-valued (negative responder) measures, this corresponds to observing an increase or decrease in the overall mean from 3.609 in group 1 to 4.175 in group 2. The sample size of 40 vaccinees per pooled group will give 80% power to detect a true difference of 0.80 standard deviations (SDs) between the mean non-zero responses and 90% power to detect a true difference of 0.90 SDs (these 2 are each conducted at a 5% alpha level). Using the mean and SD values from the HVTN 088 trial, the difference of 0.80 SDs translates to a difference of 0.313 units of  $\log_{10}$  binding magnitude; if 1 of the comparison groups has the same mean as was seen among non-negative values among vaccine recipients in the HVTN 088 trial (4.06 units), then after incorporating the expected 6% zero-valued (negative responder) measures, this corresponds to observing an increase or decrease in the overall mean from 3.722 in group 1 to 4.007 in group 2. These calculations assume a 10% loss-to-follow-up rate and the (94%) response rate observed in the HVTN 088 vaccine recipients. The same approach will be used to test superiority of the magnitude of the IgG binding Ab response to each individual gp120 antigen in the binding panel.

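### Section 6.1.2: the printed overall means imply 8–11% zeros, not the stated 6%, and Part A's 90% power at 2.04 SD is about 85–87%

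*Combined protocol and SAP*

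**What the plan says.** Section 6.1.2 sets one group of inputs for the binding magnitude-breadth endpoint. Data were "simulated assuming that the proportion of non-zero responses was 0.94 in both comparison groups". Non-zero values are normal on the log10 scale with mean 4.06 in group 1 and SD 0.391 in both groups, and 10% loss is allowed for.

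It then gives detectable differences for a two-sided Wilcoxon rank-sum test:

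- **Part A** (12 per group, alpha 5%/2): 80% power at 1.81 SD and "90% power to detect a true difference of 2.04 SDs".
- **Part B pairwise** (20 per group, alpha 5%/6): 80% power at 1.63 SD and "90% power to detect a true difference of 1.81 SDs for the pairwise comparisons".
- **Part B pooled** (40 per group, alpha 5%): 80% power at 0.80 SD and 90% at 0.90 SD.

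Each 80% difference is also expressed as a pair of overall means "after incorporating the expected 6% zero-valued (negative responder) measures". For Part A, "this corresponds to observing an increase or decrease in the overall mean from 3.691 in group 1 to 4.336 in group 2". The Part B pairwise pair is "overall mean from 3.609 in group 1 to 4.175 in group 2", and the pooled pair is "overall mean from 3.722 in group 1 to 4.007 in group 2".

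For differential memory B-cell binding, when cells cannot be pooled across participants, the section says that "power is the same (on the per-SD scale) to that calculated for binding Abs".

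**The concern.** The group 1 overall mean depends only on the response rate and the non-zero mean. It should be the same number in all three scenarios, yet three different values are printed, and none of them matches 6% zeros. If the simulation used a different zero fraction, or a different mechanism for generating zeros, the powers attached to those means are also in doubt.

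Part A matters most. Its primary binding endpoint (Section 5.1) feeds the choice of protein dose for Part B (Sections 4.5 and 4.8.1). A non-significant difference between adjacent doses will be read against the sensitivity that the plan claims.

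**Working it through.** **Means**

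With response rate p and non-zero difference d, the overall means are p × 4.06 (group 1) and p × (4.06 + d) (group 2). The printed d is 0.708, 0.637 and 0.313, so the group 2 non-zero means are 4.768, 4.697 and 4.373.

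| Scenario | Printed means | Implied p, group 1 | Implied p, group 2 | Means at p = 0.94 |
|---|---|---|---|---|
| Part A | 3.691, 4.336 | 3.691/4.06 = 0.909 | 4.336/4.768 = 0.909 | 3.816, 4.482 |
| Part B pairwise | 3.609, 4.175 | 3.609/4.06 = 0.889 | 4.175/4.697 = 0.889 | 3.816, 4.415 |
| Part B pooled | 3.722, 4.007 | 3.722/4.06 = 0.917 | 4.007/4.373 = 0.916 | 3.816, 4.111 |

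The group 1 values equal 4.06 × 10/11, 4.06 × 16/18 and 4.06 × 33/36. The denominators match the evaluable numbers after 10% loss: 12 × 0.9 = 10.8 (taken as 11), 20 × 0.9 = 18 and 40 × 0.9 = 36. The numerators are 0.94n rounded down: 10.34 to 10, 16.92 to 16 and 33.84 to 33.

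**Power**

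I simulated the two-sided Wilcoxon test (normal approximation, tie correction, 40,000 runs per cell) on a mixture of zeros and normal values. Ranges are with and without continuity correction.

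| Scenario (evaluable per arm) | Shift | Stated | Zeros fixed at 1/11, 2/18, 3/36 | Zeros random at 6% |
|---|---|---|---|---|
| Part A (11) | 1.81 SD | 80% | 79.3% | 78.0–80.0% |
| Part A (11) | 2.04 SD | 90% | 90.0% | 85.0–86.8% |
| Part B pairwise (18) | 1.63 SD | 80% | 80.2% | 84.8–85.0% |
| Part B pairwise (18) | 1.81 SD | 90% | 90.1% | 90.7–91.1% |
| Part B pooled (36) | 0.80 SD | 80% | 80.6% | 80.5–80.8% |
| Part B pooled (36) | 0.90 SD | 90% | 89.4% | 88.4–88.6% |

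Fixed counts therefore reproduce the plan's own figures.

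**Why Part A is inflated**

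Holding exactly one zero in each arm of 11 removes chance imbalance in non-responders between arms. Under a 94% response rate that configuration has probability (11 × 0.06 × 0.94^10)² = 0.126. If zeros were random at 9.1% instead, power at 2.04 SD would be only about 77–79%. So the stated 90% comes from fixing the counts, not from the zero fraction.

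**Shifts needed with random 6% zeros**

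- Part A: 80% at about 1.81–1.87 SD. For 90%, the grid gives 88.2–89.6% at 2.20 SD, 89.3–90.6% at 2.25 SD and 90.4–91.6% at 2.30 SD, so about 2.2–2.3 SD. In log10 units, 2.04 × 0.391 = 0.798 becomes 0.860 to 0.899.
- Part B pairwise: 80% at about 1.54 SD and 90% at about 1.78 SD.
- Part B pooled: 80% at about 0.79 SD and 90% at about 0.92 SD.

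**Sensitivity of Part A at 2.04 SD to evaluable n**

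- 10 per arm: 79.7–82.0%.
- 12 per arm (no loss): about 89–90%.
- Each participant lost at random with probability 10%: about 84–85%.

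**The case against.** The strongest case against is about scope and consequence.

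- **Most powers survive.** With random zeros, four of the six figures stay within about 2.5 points, and Part B pairwise at 1.63 SD is conservative. For the pooled comparison, fixed and random zeros cannot be told apart. This stands, and it limits the power error to Part A's 90% figure.
- **Whole participants.** Ten responders of 11 is the nearest whole number to 10.34, so the Part A figure could be a rounding convention. But nearest rounding would give 17/18 and 34/36 in Part B, where 16 and 33 were evidently used, and the section mentions no fixed counts.
- **The cause is not proven.** Fixed counts give group 2 means of 4.335 (Part A) and 4.009 (pooled), against the printed 4.336 and 4.007. The mismatch is in the third decimal. The cause remains an inference, but the contradiction with 6% zeros does not depend on it.
- **Evaluable n.** About 90% returns at 12 per arm, but that drops the 10% loss that the section says it assumes.
- **Dose choice.** No rule ties the Part B dose to a significant pairwise test. Safety and memory B-cell data also count, and Section 6.4.4.1 puts an overall test first. This stands, so the effect on the dose decision is indirect.
- **Memory B cells.** No zero fraction is stated for differential binding. With no zeros, power at 2.04 SD and 11 per arm is about 98%, so the carried-over figure could be conservative. That cross-reference is secondary.

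**Conclusion.** The concern holds. All three pairs of printed means contradict the 6% zeros stated in the same sentences. They imply 8.3–11.1% zeros, and a single quantity, 3.816, appears as three different values. This follows from arithmetic alone.

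Part A's 90% power at 2.04 SD is about 85–87% under the stated assumptions, taking 11 evaluable per arm and non-response occurring independently between participants. Part B pairwise power is understated at 1.63 SD, and the pooled figures barely change.

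The figures should be corrected, but the design is not undermined. The practical effect is that Part A's 90% detectable difference moves from 2.04 SD to about 2.2–2.3 SD.

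**What to change.** Rerun the simulation with zeros drawn at random (94% non-zero, independently by participant), state the evaluable n per arm, and restate the powers or detectable differences, chiefly Part A's 90% figure.

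Print 3.816 as the group 1 mean in all three places, and compute each group 2 mean as 0.94 × (4.06 + 0.391 × shift):

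- If 1.81, 1.63 and 0.80 SD are kept: 4.48, 4.42 and 4.11.
- If the 80% shifts are restated as 1.81–1.87, 1.54 and 0.79 SD: about 4.48–4.50, 4.38 and 4.11.

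If fixed zero counts were intended, state 1/11, 2/18 and 3/36 in place of 94% and 6%. In either case, bring the sentence that carries the per-SD power over to differential memory B-cell binding into line, and say what zero fraction is assumed there.

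The cost is one simulation rerun and a few sentence edits. Part A's 90% detectable difference becomes less favourable and Part B pairwise slightly more favourable. Sample size, tests and alpha levels do not change.
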